7. SAFETY ANALYSIS

7.1. General

The safety analysis set will be used for all study population summaries unless otherwise noted. Summaries will be presented for all patients.

7.2. Duration of Exposure to Study Drug

Duration of exposure to study drug (days) for individual patients is the number of days patient received drug (last day of study drug – first day of study drug + 1). Duration of treatment (days) will be summarized using descriptive statistics. Weeks on treatment using the categories ≤ 4 weeks, >4 to ≤ 12 weeks, >12 to ≤ 26 weeks, >26 to ≤ 52 weeks, >52 to ≤ 78 weeks, >78 to ≤ 104 weeks, and >104 weeks will also be summarized using descriptive statistics.

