The reader of this SAP is encouraged to read the study protocol for details on the conduct of this study, the operational aspects of clinical assessments, and the timing for completing the participation of a patient in this study.

The SAP is intended to be in agreement with the protocol, especially with regards to the primary and all secondary endpoints and their respective analyses. However, the SAP may contain more details regarding these particular points of interest, or other types of analyses (eg other endpoints). When differences exist in descriptions or explanations provided in the study protocol and this SAP, the SAP prevails; the differences will be explained in the Clinical Study Report.

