2.1. General Design

This is a multicenter, open-label study to evaluate the safety, tolerability, and efficacy of pridopidine treatment at a dosage of 45 mg bid in adults with HD. The study will consist of a screening period up to 2 weeks, followed by an open-label treatment period.

The assessments and procedures performed during each study visit are detailed in Section 3.12 of the protocol.

Up to 650 patients from the PRIDE-HD, Open PRIDE-HD, Open-HART, or future safety and efficacy clinical trials of pridopidine studies are planned to be enrolled to receive a total daily dose of 90 mg pridopidine (45 mg bid) for the duration of the study.

If medically necessary (eg following discussion with the medical monitor), the patient may be allowed to de-escalate to a dose of 22.5 mg bid. The start date and reason for de-escalation will be entered into the electronic case report form (eCRF).

In addition, patients who have already completed their defined study period under Open PRIDE-HD global or local amendments and have discontinued treatment with pridopidine can be re-enrolled and re-enter the Open PRIDE-HD study. A repeat, 2nd screening and baseline visit will be scheduled after completion of the End of Study (EoS) visit. These patients will complete the repeated (2nd) screening and baseline visit assessments (including meeting all eligibility criteria, see procedures for V1 and V2), and undergo a 1-week titration period and resume attendance of the study visits from the point at which they exited.

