4.5. Study Days and Visits

Study days are numbered relative to the first day of study drug administration. The start of treatment (Day 1) is defined as the date on which a patient takes the first dose of study drug, as recorded on the study drug diary. Days will be numbered relative to treatment start (ie, ..., -2, -1, 1, 2, ...; with day 1 being the first day of study drug administration and day -1 being the day before the first day of study drug administration).

For efficacy and safety by-visit analyses, data collected at postbaseline scheduled visits will be included using their scheduled visit, data collected at postbaseline unscheduled visits will be included and assigned to their corresponding scheduled visit, and data collected at early termination visits will be included and assigned to the next scheduled visit. After the assignments are made, if there is a scheduled and unscheduled visit at the same visit, the scheduled visit will be used in the analysis.

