7.3. Adverse Events

All AEs will be coded using the MedDRA. AEs occurring on or after the first day of study drug administration will be included in the summaries. Summaries will be presented for all AEs (overall and by severity), AEs determined by the investigator to be related to study drug (overall and by severity), serious AEs, AEs leading to withdrawal from the study, and non-serious AEs.

The incidence and total number of AEs will be summarized using descriptive statistics by SOC and PT (all AEs overall will also be presented by just PT category). For the incidence of AEs, patients are counted only once in each SOC category, and only once in each PT category. The exposure adjusted incidence rate will also be presented and is defined as the number of patients with an AE divided by patient-years of treatment. For calculating patient-years, patients with an AE contribute with treatment exposure up to the day of their first AE, and patients without an AE contribute with the entire treatment exposure. For the summary by severity, patients are counted at the greatest severity. AEs missing relationship to study drug will be included in the study drug related summary.

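### The SAP's exposure formula counts off-drug re-entry gaps as treatment, and the exposure-adjusted AE rate counts events after the last dose without the matching person-time

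*SAP*

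**What the plan says.** **Exposure.** SAP 7.2 defines duration of exposure as "the number of days patient received drug (last day of study drug – first day of study drug + 1"), and summarises it in days and in week categories up to >104 weeks.

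**Re-entry.** Under SAP 2.1, patients who finished their study period and "have discontinued treatment with pridopidine can be re-enrolled and re-enter the Open PRIDE-HD study". The sequence is set out: "A repeat, 2nd screening and baseline visit will be scheduled after completion of the End of Study (EoS) visit". They then "undergo a 1-week titration period and resume attendance of the study visits from the point at which they exited". The EoS visit is 2 weeks after the end-of-treatment visit, and no maximum gap is given.

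**Clock.** SAP 4.5 sets one origin: "The start of treatment (Day 1) is defined as the date on which a patient takes the first dose of study drug". Nothing in SAP 4.2, 4.5, 7.2 or 7.3 restarts it at re-entry or defines a treatment period.

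**AE rate.** SAP 7.3 states that "AEs occurring on or after the first day of study drug administration will be included in the summaries" and gives no closing date. The exposure-adjusted rate divides patients with an AE by treated patient-years. Patients with an AE are cut at their first event, and "patients without an AE contribute with the entire treatment exposure". By contrast, SAP 7.7 gives both a start and an end for concomitant medications.

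**Off-drug observation.** SAP 2.1 allows patients who stop for safety or tolerability to stay in the study off drug. Protocol 7.1.2 records AEs from consent to the end of the study.

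**The concern.** The words and the formula in SAP 7.2 agree only if dosing is continuous, and the SAP itself plans for interrupted treatment. A programmer who follows the formula credits a re-entrant with the whole gap. That overstates exposure, can place patients in too high a duration category, and lowers the exposure-adjusted rate to the extent that AEs are not recorded during the gap.

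The AE window has the opposite fault. A first AE in the 2-week follow-up, or in a patient who has stopped drug for good but is still attending, enters the numerator while the denominator stopped at the last dose. That raises the rate.

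As worded, the result is neither an on-treatment rate nor a follow-up rate. The exposure table and this rate are the outputs meant to allow for unequal time on drug in a study whose primary objective is safety and tolerability.

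**Working it through.** The plan gives no exposure or AE-rate figure to reproduce, so the check is algebraic with labelled assumptions.

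**1. One patient (the durations are illustrative; the result follows from the formula).** With 52 weeks on, 30 off and 26 on, time on drug is 52 + 26 = 78 weeks (category >52 to ≤78). The span is 52 + 30 + 26 = 108 weeks (category >104). With 104 + 52 weeks on drug (1092 days), gaps of 2, 26 and 52 weeks give 1106 (+1.3%), 1274 (+16.7%) and 1456 days (+33.3%).

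**2. Mean exposure.** Assume a fraction *q* re-enter after a gap of *g* years with 104 weeks on drug before and after, and everyone else has 104 weeks. The overstatement is *qg* / [4*q* + 2(1 − *q*)].
- *q* = 0.3: 0.9% for a 4-week gap; 0.3/2.6 = 11.5% for 52 weeks.
- *q* = 0.5: 1.3% for a 4-week gap; 0.5/3.0 = 16.7% for 52 weeks.

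**3. Gap effect on the rate.** Assume a constant rate *L* per patient-year, equal on and off drug. Years on drug before and after the gap are *a* and *b*. Part of the gap is AE-recorded: 2 weeks before EoS (*r1* = 2/52) and a 2-week second screening (*r2* = 2/52), because SAP 2.1 repeats the Visit 1 procedures and these include an AE inquiry. Then *u* = *g* − *r1* − *r2* is unrecorded and *T* = *a* + *b* + *r1* + *r2*.

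- Numerator = *q*(1 − e^(−LT)) + (1 − *q*)(1 − e^(−2L))
- Denominator = *q*[(1 − e^(−LT))/L + *u*·e^(−L(a+r1))] + (1 − *q*)(1 − e^(−2L))/L

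For *L* = 0.10, *a* = *b* = 2, *q* = 0.5, *g* = 1: 0.2580/2.9569 = 0.0873, which is −12.7%.

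| Re-entering | 4 wk | 13 wk | 26 wk | 52 wk |
|---|---|---|---|---|
| 10% | 0.0% | −0.7% | −1.7% | −3.7% |
| 30% | 0.0% | −1.8% | −4.4% | −9.0% |
| 50% | 0.0% | −2.7% | −6.3% | −12.7% |

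If no AE is recorded anywhere in the gap, the 50%, 52-week case becomes −13.8%. With 52 weeks on drug before and after instead of 104, and the same recorded weeks, it becomes −18.4%.

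**4. Off-drug AEs.** A fraction *p* stop at Week 26. A fraction *s* of them stay to Week 106, and those who leave have 2 recorded weeks.

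- Numerator = (1 − *p* + *ps*)(1 − e^(−L·106/52)) + *p*(1 − *s*)(1 − e^(−L·28/52))
- Denominator = (1 − *p*)(1 − e^(−2L))/L + *p*(1 − e^(−0.5L))/L

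At *L* = 0.10:
- *p* = 0 (2-week follow-up alone): 0.1844/1.8127 = 0.1017, +1.7%.
- *p* = 0.1: +5.8% (*s* = 0.5) and +9.8% (*s* = 1).
- *p* = 0.2: +10.6% (*s* = 0.5) and, for *s* = 1, 0.1844/1.5477 = 0.1192, +19.2%.

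The results for *p* > 0 include the 1.7%.

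**5. Both together.** Re-entrants (*q*), stoppers (*p*) and the rest (1 − *q* − *p*) are taken as disjoint shares of the cohort, all with 2 weeks of final follow-up. Re-entrants have numerator 1 − e^(−L(T+2/52)) and the step 3 denominator. Stoppers and the rest are as in step 4.
- Lowest: *q* = 0.5, 52-week gap, *p* = 0.1, *s* = 0.5 gives 0.2543/2.8244 = 0.0900, −10.0%.
- Highest: *q* = 0.3, 4-week gap, *p* = 0.2, *s* = 1 gives 0.2303/2.0083 = 0.1147, +14.7%.
- If stoppers are instead a share of the non-re-entrants, the range is −10.9% to +10.3%.

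**6. A common AE (*L* = 1.0).** Gaps give 0% to −6.1%, follow-up alone +0.6%, stoppers +3.6% to +12.9%, and both together −3.5% to +12.2%. Most first events happen early, so the effects shrink.

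Temporary interruptions within a period (Protocol 5.5) create no numerator mismatch, because AEs are recorded throughout. They only mean that the span is not literally days on drug.

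**The case against.** The strongest reply is that re-entry appears only in the SAP. The supplied protocol (Amendment 02) has up to 300 patients and a fixed 104 weeks of treatment. The SAP has up to 650 and open-ended visits, so it evidently follows a later protocol that may settle consent, AE recording and dose logging at re-entry. If AEs were recorded throughout the gap, the downward effect on the rate would disappear under the constant-rate model. This stands as a limit on the size: the unrecorded gap is inferred from the consent-to-end-of-study rule in Protocol 7.1.2, and SAEs that come to the investigator's notice after treatment are still reported. It does not repair the exposure formula, and the SAP claims precedence: "When differences exist in descriptions or explanations provided in the study protocol and this SAP, the SAP prevails".

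Other points also stand in part. With 104 weeks on drug before re-entry, both calculations already fall in the >104 category, so misclassification needs an earlier exit, such as at 52 weeks. The +19.2% needs every early stopper to remain off drug to Week 106, although staying is optional and limited to safety or tolerability stops. The AE window is not unlimited in practice, since recording ends with the study; the narrower and valid point is that this end is not tied to the last dose. Finally, the study is descriptive and untested, and the crude AE, SAE, withdrawal and tolerability outputs do not use this denominator.

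**Conclusion.** The concern holds. The formula in SAP 7.2 contradicts its own description as soon as a patient re-enters, and the numerator and denominator of the SAP 7.3 rate cover different days. These are rules that give a wrong result, not just missing detail.

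The wording faults are certain, but their size is not. With few re-entrants and gaps near 4 weeks, the gap effect on the rate is negligible. With many re-entrants and long gaps, or many patients followed off drug, the rate can be wrong by roughly a tenth or more in either direction. The two errors need not cancel. All percentages for the cohort rest on assumed shares, gap lengths and a constant AE rate equal on and off drug. The point should be fixed before lock, but its scope is modest: one exposure table and one adjusted rate.

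**What to change.** **SAP 7.2.** Define a treatment period as running from its first to its last dose, with a new period starting at each re-entry after an EoS visit. Define exposure as the sum over periods of (last day − first day + 1), with temporary interruptions inside a period included. If days actually dosed are also wanted, give them as a supplementary summary, and only if stop and restart dates are in the eCRF.

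**SAP 7.3.** Make the AE window and the person-time of the exposure-adjusted rate cover the same days. One workable rule runs from the first dose of each period to its last dose plus the 2-week follow-up, ending earlier at the last study contact or the next period's first dose. Person-time is those same days, cut at the first AE. A strict on-drug window for both would match equally well. The text should also say whether an AE in an excluded off-drug stretch ends a re-entrant's time at risk. Tabulate later off-drug AEs separately and leave the all-AE crude tables unchanged, so that no event is lost from the report.

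**Cost.** SAP wording and programming before database lock, with no new visits. The present formula needs one pair of dose dates per patient and the corrected one needs a pair per period, so confirm that the data source holds them.

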7.3. Adverse Events

All AEs will be coded using the MedDRA. AEs occurring on or after the first day of study drug administration will be included in the summaries. Summaries will be presented for all AEs (overall and by severity), AEs determined by the investigator to be related to study drug (overall and by severity), serious AEs, AEs leading to withdrawal from the study, and non-serious AEs.

The incidence and total number of AEs will be summarized using descriptive statistics by SOC and PT (all AEs overall will also be presented by just PT category). For the incidence of AEs, patients are counted only once in each SOC category, and only once in each PT category. The exposure adjusted incidence rate will also be presented and is defined as the number of patients with an AE divided by patient-years of treatment. For calculating patient-years, patients with an AE contribute with treatment exposure up to the day of their first AE, and patients without an AE contribute with the entire treatment exposure. For the summary by severity, patients are counted at the greatest severity. AEs missing relationship to study drug will be included in the study drug related summary.

7.4. Clinical Laboratory Tests

Laboratory test results will be presented in standard international (SI) units.

Summary statistics for serum chemistry, hematology, and urinalysis laboratory tests will be presented at baseline and each visit. Laboratory tests values and changes from baseline to each visit will be summarized using descriptive statistics.

Shifts (below, within, and above the normal range) from baseline to each visit will be summarized using patient counts.

The incidence of potentially clinically significant abnormal values will be summarized for laboratory tests using descriptive statistics with the criteria specified in [Table 1](#). These summaries will include all postbaseline values (including scheduled, unscheduled, and early termination visits).

Table 1: Criteria for Potentially Clinically Significant Laboratory Values

| Test | Criterion value |
|-------------------------------------|---|
| Serum chemistry | |
| Alanine aminotransferase (ALT) | ≥3x ULN |
| Aspartate aminotransferase (AST) | ≥3x ULN |
| Alkaline phosphatase | ≥3x ULN |
| Gamma-glutamyl transpeptidase (GGT) | ≥3x ULN |
| Lactate dehydrogenase (LDH) | ≥3x ULN |
| Blood urea nitrogen (BUN) | ≥10.71 mmol/L |
| Creatinine | ≥177 μmol/L |
| Uric acid Men | ≥625 μmol/L |
| Women | ≥506 μmol/L |
| Bilirubin (total) | ≥34.2 μmol/L |
| Hematology | |
| Hematocrit Men | <0.37 L/L |
| Women | <0.32 L/L |
| Hemoglobin Men | ≤115 g/L |
| Women | ≤95 g/L |
| White blood cell (WBC) counts | ≤3 x 10 ⁹ /L ≥20 x 10 ⁹ /L |
| Eosinophils | ≥10% |
| Absolute neutrophil counts (ANC) | ≤1 x 10 ⁹ /L |
| Platelet counts | ≤75 x 10 ⁹ /L ≥700 x 10 ⁹ /L |
| Urinalysis | |
| Blood (HGB) | ≥2 unit increase from baseline |
| Glucose | ≥2 unit increase from baseline |
| Total protein | ≥2 unit increase from baseline |

ULN=upper limit of normal

7.5. Vital Signs

Summary statistics for pulse, blood pressure (supine/sitting and standing), body temperature, weight, and orthostatic blood pressure (supine/sitting – standing value) will be presented at baseline and each visit. Vital signs values and changes from baseline to each visit will be summarized using descriptive statistics.

The incidence of potentially clinically significant abnormal values will be summarized for vital signs using descriptive statistics with the criteria specified in [Table 2](#). These summaries will include all postbaseline values (including scheduled, unscheduled, and withdrawal visits). Note that in order to qualify as potentially clinically significant abnormal, a value needs to meet both criteria below: ie, have a value beyond the criterion value and a change of at least the magnitude specified in the change relative to baseline column.

Table 2: Criteria for Potentially Clinically Significant Vital Signs

| Vital Sign | Criterion value | Change relative to baseline |
|--------------------------|-----------------|-----------------------------|
| Pulse | ≥120 bpm | Increase of ≥15 |
| | ≤50 bpm | Decrease of ≥15 |
| Systolic blood pressure | ≥180 mm Hg | Increase of ≥20 |
| | ≤90 mm Hg | Decrease of ≥20 |
| Diastolic blood pressure | ≥105 mm Hg | Increase of ≥15 |
| | ≤50 mm Hg | Decrease of ≥15 |
| Body temperature | ≥38.3°C | Change of ≥1.1°C |
| Orthostatic SBP (mmHg) | >= 20 mmHg | |
| Orthostatic DBP (mmHg) | >= 10 mmHg | |

7.6. Electrocardiography

Shifts (normal and abnormal) from baseline to overall finding and each visit will be summarized using patient counts. For overall finding, the summary will use the worst postbaseline finding for the patient (the abnormal finding if there are both normal and abnormal findings). Summary statistics for ECG variables will be presented at baseline and each visit. Actual values and changes from baseline to each visit will be summarized using descriptive statistics.

The incidence of potentially clinically significant abnormal values for ECG variables will be summarized using descriptive statistics with the criteria specified below.

- QTcF values >450 msec or >480 msec or >500 msec.
- QTcF change from baseline values >30 or >60.
- PR change from baseline ≥25% and value >200.
- QRS change from baseline ≥25% and value >110.
- Heart rate value <60 bpm or >100 bpm.

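### Chemistry, hematology, absolute QTcF and ECG heart-rate counts of potentially clinically significant values do not separate new from pre-existing cases, and ECG heart rate and pulse follow different, unexplained rules

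*SAP*

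**What the plan says.** SAP 7.4, 7.5 and 7.6 each plan an incidence of potentially clinically significant values.

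- **Laboratory (7.4).** The table "Criteria for Potentially Clinically Significant Laboratory Values" gives absolute limits for chemistry and hematology. Its three urinalysis rows instead require a rise of at least 2 units from baseline. On which values count: "These summaries will include all postbaseline values (including scheduled, unscheduled, and early termination visits").
- **Vital signs (7.5).** "Note that in order to qualify as potentially clinically significant abnormal, a value needs to meet both criteria below", that is, a value limit and a change from baseline. For pulse this means ≤50 bpm with a fall of ≥15, or ≥120 bpm with a rise of ≥15. The change cell is empty in the two orthostatic rows.
- **ECG (7.6).** Two lines are absolute: "QTcF values >450 msec or >480 msec or >500 msec" and "Heart rate value <60 bpm or >100 bpm". Three refer to baseline: "QTcF change from baseline values >30 or >60", "PR change from baseline ≥25% and value >200" and "QRS change from baseline ≥25% and value >110".

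SAP 4.2 defines baseline as the last observation before the first dose in this study for PRIDE-HD patients. For Open-HART patients it is the last observation before the first dose in Open-HART.

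**The concern.** Safety and tolerability are the primary objective, and the study has no control arm from which to judge background frequency. An incidence table is normally read as what arose on treatment. Where the criterion is a bare threshold, the count mixes patients who crossed the limit after dosing with patients who were already beyond it and stayed there. The SAP conditions on baseline for most other criteria, so the omission here looks like an inconsistency in convention, and no reason is given.

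Rate is a special case. Much the same quantity is judged by two rules under one label: pulse needs an extreme value and a change, while ECG heart rate needs only a value, at a less extreme limit. The two tables can then give very different pictures of the same patients.

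**Working it through.** The plan states no incidence, heart-rate mean or SD, so there is no figure to reproduce. The check has three parts.

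**1. Which criteria carry a baseline condition**

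| Group | Refers to baseline | Does not |
|---|---|---|
| Chemistry and hematology (Table 1) | 0 | 20, counting sex-specific and low/high limits separately |
| Urinalysis (Table 1) | 3 | 0 |
| ECG lines (7.6) | 3 (QTcF change, PR, QRS) | 2 (absolute QTcF, heart rate) |
| Pulse, blood pressure, temperature (Table 2) | all | none |
| Orthostatic rows (Table 2) | change cell empty | 2 |

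**2. Whether another planned table recovers the split**

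- Laboratory shifts are against the normal range. A patient going from just above normal to ≥3× ULN moves from above to above. So does one who was at ≥3× ULN throughout. The table cannot tell them apart.
- ECG shifts use the overall normal/abnormal finding, not heart rate or the QTcF limits.
- Changes from baseline by visit describe the group, not who crossed a limit.

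**3. Size, for heart rate only (illustrative)**

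Assumed, not from the documents: normal heart rate rounded to whole bpm, mean 65, 70 or 75, total SD 9 or 11, within-patient correlation ρ of 0.5 or 0.7, no drug effect. Patient i at visit j has mean + bᵢ + eᵢⱼ, with Var(b) = ρ·SD² and Var(e) = (1−ρ)·SD². There is one baseline and 7 post-baseline ECGs (Protocol Table 1: weeks 4, 12, 26, 52, 78, 104, 106), with 400,000 simulated patients per scenario. A patient counts if any post-baseline value meets the rule. SAP 7.4 and 7.5 say this. SAP 7.6 does not repeat it, so it is inferred there.

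| Mean | Any <60 bpm | ≤50 and fall ≥15 | Of those <60, already <60 at baseline | New <60 among baseline ≥60 |
|---|---|---|---|---|
| 65 | 55.5–70.6% | 2.6–14.8% | 37.5–48.3% | 41.4–60.8% |
| 70 | 31.9–49.8% | 1–8% | 24.8–37.8% | 24.2–42.4% |
| 75 | 13.9–29.1% | 0.3–3.7% | 15.7–29.2% | 11.0–25.2% |

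Across scenarios the two low rules differ by a factor of about 5 (0.706/0.1484) to 42 (0.139/0.0033). On the high side, any value >100 flags 0.02–5.3%, against less than 0.02% for ≥120 with a rise of ≥15.

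One scenario shows the mixture (mean 70, SD 11, ρ = 0.7). The count as written is 40.5%. Pre-existing part: 0.405 × 0.378 = 15.3 points. New part: baseline ≥60 is 1 − 0.169 = 0.831 of patients, and 0.831 × 0.303 = 25.2 points. The sum is 40.5. New-onset incidence on the right denominator is 30.3%. The baseline split therefore removes part of the count but not the effect of the 60 bpm limit, which is why the rate rules need separate attention.

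**The case against.** - **Most of the ECG lines, and urinalysis, are conditioned.** A reader might infer that laboratory and ECG counts in general ignore baseline. The documents do not support that: three of five ECG lines and all three urinalysis rows refer to it.
- **Other outputs stand beside the counts.** A reader might infer that a drug signal could not be seen at all. That goes too far. QTcF change limits follow the absolute ones, changes from baseline are summarized at each visit, and Protocol 9.7.2 plans listings of laboratory and vital-sign values beyond the boundaries. A mean fall in heart rate would show. No test or formal decision rests on these counts.
- **Entry criteria limit pre-existing abnormality.** Protocol 4.2 excludes QTcF >450 msec, creatinine clearance <60 mL/min and clinically significant laboratory results. This is substantial. By the protocol's clearance formula, a man aged 45 at the creatinine limit of 177 μmol/L (about 2.0 mg/dL) would have to weigh at least 60 × 72 × 2.002/95 ≈ 91 kg to qualify. It is not complete, though. The QTcF exclusion uses the mean of three screening readings, while later ECGs are single and baseline is the last value before dosing. The laboratory exclusion is a matter of investigator judgment, not tied to Table 1. For Open-HART patients the SAP baseline precedes Open-HART dosing, so screening here does not govern it.
- **A sensitive ECG screen is defensible.** A reader might conclude that the ECG limits should be replaced by the pulse pair, or that normal values are being called abnormal. The documents give no heart-rate reference range, and replacement has a cost: a patient going from 58 to 45 bpm falls by 13, less than 15, and would be missed.
- **The orthostatic variable is already a within-visit difference.** An empty change cell most naturally means that no change is required. That needs a clarifying clause, nothing more.

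**Conclusion.** The point holds for four groups of counts: chemistry, hematology, absolute QTcF and ECG heart rate. For these, the planned incidence includes patients already beyond the limit at the SAP 4.2 baseline, and no other planned summary table separates them at the same limit. In an uncontrolled study with safety as its primary objective, that makes the tables harder to interpret. It biases no test and changes no sample size.

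The laboratory and QTcF effect cannot be sized without the share of patients beyond each limit at baseline, which the documents do not give. The entry criteria suggest that it is limited. The heart-rate figures (about 14–71% flagged at <60 bpm with no drug effect, against 0.3–15% by the low-pulse rule) rest wholly on the assumed means, SDs and correlations and on counting any of 7 ECGs. The direction of the gap is stable across those assumptions, but its level is not. The change is worth making because it is cheap.

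**What to change.** 1. **SAP 7.4 (chemistry, hematology) and 7.6 (absolute QTcF, heart rate).** Keep the all-patient count. Add counts split by whether the limit was met at the SAP 4.2 baseline, with patients who did not meet it as the denominator for new-onset incidence.
2. **Open-HART patients.** Show them separately or footnote them. Because their baseline precedes the first Open-HART dose, a limit not met at that baseline and met later need not be new in this study.
3. **Rate criteria.** Keep the ECG heart-rate limits, and reconcile or explain the difference from pulse in 7.5, for example by also tabulating ECG heart rate by the 7.5 criteria.
4. **SAP 7.6.** State which post-baseline ECGs enter the counts, as 7.4 and 7.5 do.
5. **SAP Table 2.** State that the orthostatic rows need the criterion value only, if that is intended.

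The cost is SAP wording, one derived baseline flag and an extra column. No new data are needed. New-onset counts will be smaller than the all-patient counts, which is why both should be shown. These are reporting criteria and do not touch patient management.
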